9.5.2 Appropriateness of Measurements

The testing methods are based on the standardized test method ASTM E1173-15, *Evaluation of Preoperative, Precatheterization, or Preinjection Skin Preparations*. The effectiveness criteria are that the \log_{10} recoveries of the two test products (26 mL and 5.1 mL) are non-inferior to the Positive Control (Prevantis® Maxi Swabstick 5.1 mL) by no more than the upper margin of the 95% confidence interval of a 0.5 margin (\log_{10} scale) per square centimeter on the abdominal and inguinal sites within 30 seconds after drying and within 10 minutes after drying. To show persistence of effect for the test materials, the 6 hours post-treatment measurement should be lower than or equal to the baseline measurement for 100 percent of the subjects on the abdominal and inguinal sites. The efficacy criteria will be consistent with the requirements of the 2017 FDA 21 CFR Part 310, *Safety and Effectiveness of Health Care Antiseptics; Topical Antimicrobial Drug Products for Over-the-Counter Human Use*, Final Rule (December 20, 2017).

9.5.2.1 Neutralization

A neutralization study will be performed to assure that the neutralizers used in the recovery medium quench the antimicrobial activity of each test material and are not toxic to the challenge species. The study will comprise both an *In-vivo* component performed using human subjects, and an *In-vitro* component performed based on ASTM E1054-08(2013), *Standard Test Methods for Evaluation of Inactivators of Antimicrobial Agents*. *Escherichia coli* (ATCC 11229), *Staphylococcus aureus* (ATCC 6538) and methicillin-

PROTOCOL #1810480-103.01

Page 20 of 43

BIOSCIENCE LABORATORIES, INC.

This Protocol has been approved by the GIRB on 03/06/19

resistant *Staphylococcus aureus* MRSA (ATCC 33591) will be used as the challenge species in both components of the neutralizer validation study. Reference Appendix 4 for the procedure for validation of neutralization effectiveness.

9.5.3 Primary Efficacy Variables

The primary efficacy variables for this study are the immediate antimicrobial effects at 30-seconds and 10-minutes post-application and persistent antimicrobial effects at 6-hours post-application. The effectiveness criteria are that the \log_{10} recoveries of the two test products (26 mL and 5.1 mL) are non-inferior to the Positive Control (Prevantics® Maxi Swabstick 5.1 mL) with a 0.5 margin (\log_{10} scale) per square centimeter on the abdominal and inguinal sites within 30 seconds after drying and within 10 minutes after drying. The determination of non-inferiority will be based on the regression model used with a 95% confidence interval around the Average Treatment Effect (ATE). The upper bound of the 95% confidence interval cannot exceed 0.5. To show persistence of effect for the test materials, the 6-hours post-treatment measurement should be lower than or equal to the baseline measurement for 100 percent of the subjects on the abdominal and inguinal sites. The efficacy criteria will be consistent with the requirements of the 2017 FDA 21 CFR Part 310, *Safety and Effectiveness of Health Care Antiseptics; Topical Antimicrobial Drug Products for Over-the-Counter Human Use*, Final Rule (December 20, 2017).

9.5.4 Data Collection and Microbial Recoveries

Colonies will be manually counted and data recorded on appropriate data collection forms. If one of the plates is uncountable, the count on the remaining plate will be used for calculations and noted in the source record.

The estimated \log_{10} number of viable microorganisms recovered from each sample site will be designated the “R-value.”

To convert the volumetric measure of the sample into the number of colony-forming units per square centimeter (cm^2), the following formula will be employed:

$$R = \log_{10} \left[\frac{F \left(\frac{\sum c_i}{n} \right) 10^{-D}}{A} \right]$$

where:

R = the average colony-forming unit count in \log_{10} scale per cm^2 of sampling surface

F = total number of mL of stripping fluid added to the sampling cylinder; in this study, $F = 6 \text{ mL}$

$$\frac{\sum c_i}{n} = \text{average of the triplicate colony counts used for each sample collected}$$

D = dilution_factor of the plate counts

A = inside area of the cylinder in cm^2 ; in this study, $A = 3.46 \text{ cm}^2$

NOTE: The reason that a \log_{10} transformation will be performed on the collected data is to obtain a linear scale. A linear scale, more appropriately a \log_{10} linear scale, is a basic requirement of the statistical models used in this study.

Average colony counts ($\frac{\sum c_i}{n}$) of 0 will be set to 0.5 prior to calculating R -values. Any

calculated CFU/cm^2 values ($\frac{F(\frac{\sum c_i}{n})10^{-D}}{A}$) of less than 1 will be set to 1 CFU/cm^2 , such that the \log_{10} transformation will be zero for the calculated R -Value.

Data collected from subjects with low or high test-day baseline counts on an anatomical test site ($< 3.0 \log_{10} \text{CFU}/\text{cm}^2 > 5.5 \log_{10} \text{CFU}/\text{cm}^2$ from the skin of the abdomen, or $< 5.0 \log_{10} \text{CFU}/\text{cm}^2 > 7.5 \log_{10} \text{CFU}/\text{cm}^2$ on the skin on the inguen) will not be used in the Efficacy Analyses (Section 9.7.1). This is a common occurrence in clinical-simulation studies. Hence, more subjects will be enrolled and tested to account for test-day baseline failures.

9.6 Data Quality Assurance

The Sponsor's designated Quality Assurance Representative may conduct audits at the study site. Audits will include, but are not limited to test materials, presence of required documents, the informed consent process, and review of source documents. The Investigator agrees to participate with audits conducted at a reasonable time in a reasonable manner.

The study will be inspected by Quality Assurance at BioScience Laboratories, Inc., and reports will be submitted to the Principal Investigator and Management in accordance with BioScience Laboratories, Inc., Standard Operating Procedures.

9.7 Statistical Methods and Determination of Sample Size

The statistical analysis will be performed by BSLI statistician, [name], to determine the correct sample size to use for the abdominal and inguinal sites with a Beta error of 0.20 (Power of $1 - 0.20 = 0.80$), an alpha error of 0.05, and a detectable difference of 0.5. The PASS Version 16 statistical package will be used to determine the number of subjects needed in the pivotal study in order to pass the evaluation.

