7.0 INTRODUCTION

Prior to surgery or other invasive procedures, skin must be treated with a topical antimicrobial product to minimize the risk of nosocomial infection by reducing the number of microorganisms on the skin. The 2017 FDA 21 CFR Part 310, *Safety and Effectiveness of Health Care Antiseptics; Topical Antimicrobial Drug Products for Over-the-Counter Human Use*, Final Rule requires that the immediate and 10-minute \log_{10} recoveries of the test product is non-inferior to an positive control by a margin of 0.5 \log_{10} , superior to that of a negative control by a margin of 1.2 \log_{10} , and that 100% of subjects' microbial populations recovered in the 6-hour samples are less than baseline populations. The testing methods for performing such evaluations are also described in the standardized test method ASTM E1173-15, *Evaluation of Preoperative, Precatheterization, or Preinjection Skin Preparations*.

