8.0 STUDY OBJECTIVES

The purpose of this pilot study is to evaluate the antimicrobial efficacy of two test products containing a chlorhexidine gluconate and isopropyl alcohol solution (26 mL and 5.1 mL), when used as a patient preoperative skin preparation. The evaluation will determine the correct application procedures and the number of subjects needed to pass the pivotal study. The \log_{10} recoveries of the normal flora will be used to determine the antimicrobial effectiveness of the two test products consistent with the requirements of the 2017 FDA 21 CFR Part 310, *Safety and Effectiveness of Health Care Antiseptics; Topical Antimicrobial Drug Products for Over-the-Counter Human Use*, Final Rule (December 20, 2017).

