9.0 INVESTIGATIONAL PLAN

9.1 Overall Study Design and Plan

This pilot study is designed to determine the antimicrobial effectiveness of two test products (Test Products #1 and #2), intended for use as Patient Preoperative Skin Preparations. The testing methods are based on the standardized test method ASTM E1173-15, *Evaluation of Preoperative, Precatheterization, or Preinjection Skin Preparations*, and using the requirements specified by the 2017 FDA 21 CFR Part 310, *Safety and Effectiveness of Health Care Antiseptics; Topical Antimicrobial Drug Products for Over-the-Counter Human Use*, Final Rule (December 20, 2017). The immediate and persistent antimicrobial effects will be measured to evaluate the efficacy.

At least 75 subjects will be treated bilaterally with two of the three test materials (Test Product #1, Test Product #2, and Positive Control), one per each side of the abdomen and inguinal test sites. Subjects will be required to complete a 14-day pre-test conditioning period. Subjects will complete a 1-day test period, during which time subjects' sites will be treated with the test materials and samples taken following treatment. The Cylinder Sampling Technique will be performed for baseline and for sampling 30-seconds, 10-minutes, and 6-hours post-test material-application on Test Day.

The effectiveness criteria are that the \log_{10} recoveries of the two test products (26 mL and 5.1 mL) are non-inferior to the Positive Control (Prevantics® Maxi Swabstick 5.1 mL) with a 0.5 margin (\log_{10} scale) per square centimeter on the abdominal and inguinal sites within 30 seconds after drying and within 10 minutes after drying. The determination of non-inferiority will be based on the upper bounds of the 95% confidence interval being equal to or less than 0.5. Superiority will not be evaluated in this study. To show persistence for the test materials, the 6 hours post-treatment measurement should be lower than or equal to the baseline measurement for microbial reductions for 100 percent of the subjects on the abdominal and inguinal sites. This evaluation will determine the correct application procedures and the power for the pivotal study.

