9.4.3 Method of Assigning Subjects to Treatment Groups

The three test materials will be assigned randomly to the test sites per a computer-generated randomization schedule, such that two of the three test materials are used on each subject at the abdomen and/or inguinal sites, one test material on one side, and another test material on the opposite side of the subject. The randomization schedule will be continued until it is determined that the required sample sizes are fulfilled.

The specific sites for post-application sampling (i.e., 30 seconds, 10 minutes, and 6 hours after skin preparation on the abdominal and inguinal test sites) will be assigned according to a computer-generated randomization scheme.

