9.7.1 Statistical Methods

The Minitab® Version 18 statistical computer package will be used for all statistical calculations.

Non-Inferiority Analysis

An analysis of the data will be performed to determine the non-inferiority of the two test products to the Positive Control. Separate analyses will be performed for data sets for both the abdomen and the inguinal test sites and for the 30-seconds and 10-minutes post-application sample time. Only those data from sites meeting the baseline criteria (3.0 - 5.5 \log_{10} CFU/cm² from the skin of the abdomen and 5.0 - 7.5 \log_{10} CFU/cm² from the skin of the inguen) will be used in the analysis.

The statistic to be used is a multiple linear regression with one quantitative and one qualitative predictor. It has the form:

$$\hat{y} = B_0 + B_1 x_1 + B_2 x_2 + e$$

where:

\hat{y} = \log_{10} Recoveries

B_0 = y intercept

B_1 = Regression slope

B_2 = Difference between the two products

x_1 = \log_{10} Baseline

x_2 = Products

1, if Test Product

2, if Positive Control

e = Error term

The average treatment effect (ATE) is the mean of the 95% confidence interval. For the non-inferiority test, the upper bound of the 95% confidence interval must be equal to or less than 0.5 \log_{10} .

For the non-inferiority test:

$$\bar{x}_C - \bar{x}_T \leq 0.5$$

where:

\bar{x}_T = mean of the test product

\bar{x}_C = mean of the positive control product

0.5 = non-inferiority margin

Descriptive statistics will be generated, including sample sizes, means, standard deviations, and ranges of the recovery data.

Sample Size Determination Analysis

When the study is complete, the PASS 16 statistical package will determine the number of subjects used in a pivotal study for the abdominal and inguinal regions.

The formula that will be used is:

$$n \geq \frac{2 s^2 (z_{\alpha/2} + z_{\beta})^2}{0.5^2}$$

where:

n = minimum number of subjects employed in the study

2 = number of products tested; 3 test materials (Test Product #1, Test Product #2 and Positive Control)

s^2 = the largest variance of the two products tested at the abdominal or inguinal sites

$z_{\alpha/2} = 1.96$ (z-scale) for $1 - 0.05 = 95\%$ confidence of Type I error

$z_{\beta} = 0.842$ (z-scale) for $1 - 0.20 = 0.80\%$ confidence of Type II error

0.5 = Detection level requirement

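### The pivotal sample size gives 0.80 power for one site-by-time comparison at zero true difference, but it is described as the number needed to pass, which takes four non-inferiority comparisons per test product

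*Combined protocol and SAP*

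**What the plan says.** The combined protocol and SAP makes sizing the pivotal study an aim of this pilot. Section 8.0 says the evaluation will find "the number of subjects needed to pass the pivotal study". Section 9.1 says it will settle "the correct application procedures and the power for the pivotal study". Section 9.7 sets beta 0.20, alpha 0.05 and a detectable difference of 0.5 log10, and will use the result to "determine the number of subjects needed in the pivotal study in order to pass the evaluation".

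Section 9.7.1 gives the formula, n ≥ 2s²(z_α/2 + z_β)²/0.5², with z values 1.96 and 0.842. Here s² is "the largest variance of the two products tested at the abdominal or inguinal sites", and the denominator is defined as "0.5 = Detection level requirement". The formula has no term for a true difference and none for more than one comparison.

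The criteria in 9.1, 9.5.2 and 9.5.3 ask for non-inferiority "on the abdominal and inguinal sites within 30 seconds after drying and within 10 minutes after drying", and 9.7.1 analyses each site and time separately. Sections 9.2 and 9.7.2 give 100 per material as the minimum for a pivotal study and use the pilot to judge whether 100 would be enough.

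**The concern.** Power of 0.80 for one comparison is not a 0.80 chance of passing when four comparisons must all succeed. Unless the four results move together perfectly, or the other three have power to spare, the joint probability is lower. A sponsor who takes n as the number needed to pass could start a pivotal study whose chance of meeting every non-inferiority criterion is below 0.80. The pilot could also answer yes on 100 per material when a joint calculation would not support it.

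**Working it through.** **Inputs from the documents.** Margin 0.5 log10; z values 1.96 and 0.842; four comparisons per test product; at least 100 per material. I read n as per material, which is what a two-group formula of this form gives.

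**Assumptions, because the documents are silent.** The SD, a common correlation r among the four test statistics, the true difference d (positive means the test product is worse), and independence between materials, as in the formula.

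**1. The plan's own figure.** n = 2 × SD² × (1.96 + 0.842)² / 0.25 = 62.81 × SD². That is 63 at SD 1.0, 76 at 1.1, 91 at 1.2 and 100 at 1.26. Φ(0.842) = 0.800, so the stated power is reproduced for one comparison. With the whole margin in the denominator, d is zero.

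**2. Joint power.** For each comparison, t = (0.5 − d)/(SD × √(2/n)) − 1.96, and its power is Φ(t). Joint power is the probability that four standard normal variables with correlation r all fall below their thresholds. At r = 0 it is Φ(t)⁴. Example at n = 100, SD 1.2: t = 0.5/(1.2 × 0.1414) − 1.96 = 0.986, Φ(t) = 0.838, and 0.838⁴ = 0.493.

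**3. Results at n = 100, equal variances, d = 0.** This is the relevant case up to SD 1.26, because 100 is a minimum.

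| SD | Formula n | One comparison | All four, r = 0 | r = 0.5 | r = 0.9 |
|---|---|---|---|---|---|
| 1.0 | 63 | 0.94 | 0.79 | 0.84 | 0.90 |
| 1.1 | 76 | 0.90 | 0.64 | 0.73 | 0.83 |
| 1.2 | 91 | 0.84 | 0.49 | 0.62 | 0.75 |
| 1.26 | 100 | 0.80 | 0.41 | 0.56 | 0.70 |

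Above SD 1.26 the formula asks for more than 100, but joint power stays about the same. At SD 1.5 and n = 142 it is 0.41, 0.56 and 0.70 (rounded down from 0.705) for the three correlations.

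**4. SD at which joint power at n = 100 falls below 0.80.**

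| True difference | r = 0 | r = 0.5 | r = 0.9 |
|---|---|---|---|
| Zero | 0.99 | 1.04 | 1.14 |
| Test product 0.1 log10 worse | 0.79 | 0.83 | 0.91 |
| Test product 0.1 log10 better | 1.19 | 1.24 | 1.37 |

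The formula's own cut-off for 100 is 1.26.

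**5. Features that narrow the gap, at the formula's n, d = 0.**

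| Assumption | r = 0 | r = 0.5 | r = 0.9 |
|---|---|---|---|
| Equal variances | 0.41 | 0.56 | 0.70 |
| Other site has half the variance | 0.61 | 0.68 | 0.75 |
| Other three comparisons have half the variance | 0.75 | 0.78 | 0.80 |
| s² unadjusted, baseline explains 20% | 0.60 | 0.70 | 0.81 |
| Baseline 20% and other site at half variance | 0.76 | 0.80 | 0.84 |

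In the last row the gap closes at about r = 0.5 and reverses above it. Section 9.7.1 does not say whether s² is the raw or the baseline-adjusted variance. If it is already adjusted, the last two rows do not apply.

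**The case against.** The strongest reply is that nothing shows the pivotal study falls in the affected range. With 100 per material as a floor, there is essentially no shortfall up to an SD of about 1.0, and the documents give no SD. This stands. The low figures near 0.41-0.70 belong only to SDs of about 1.26 and above, and then only with equal variances.

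Second, the plan has some protection. It uses the largest variance and its analysis adjusts for baseline. Also, "two of the three test materials are used on each subject at the abdomen and/or inguinal sites", so some subjects carry both test and control, and the correlation between their two sides may narrow the gap further if the pivotal study keeps this design. This stands too, but none of it makes 0.80 the probability of passing all four.

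Third, the wording is ordinary power language, no sentence equates 0.80 with the chance of meeting every criterion, and 9.7.2 does not tie its judgement on 100 to the formula alone. That is fair as to intent. Even so, 8.0 and 9.7 do describe the resulting n by reference to passing, and no section supplies the joint figure.

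A reader might infer more: that the formula is miscalculated, that the pivotal study will be underpowered, or that the pilot's error rate is affected. The documents support none of these. The formula is right for one comparison. A shortfall depends on values not yet known. Requiring every comparison to succeed does not inflate type I error.

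**Conclusion.** The mismatch is real. The property claimed for n, that it is enough to pass, is not the one the formula delivers. How much this matters is conditional. With equal variances and zero true difference, the SDs at risk of a wrong yes on 100 run from about 0.99-1.14 (depending on r) up to 1.26. A true difference of 0.1 log10 moves the lower end down to 0.79-0.91 or up to 1.19-1.37, depending on its direction. In favourable combinations of variances, baseline adjustment and correlation there is no gap.

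These figures cover one test product and non-inferiority only. They leave out the 6-hour persistence criterion and the comparison listed in 7.0, "superior to that of a negative control by a margin of 1.2", which this pilot does not evaluate. The change is worth making because sizing the pivotal study is a stated objective, but it is a planning and labelling matter.

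**What to change.** In 9.7 and 9.7.1, label 0.80 as 'power for a single site-by-time comparison at zero true difference'. In 8.0 and 9.7, do not describe that n as the number needed to pass. Add to 9.7.1:

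> For each test product, the joint probability of passing all four non-inferiority comparisons will be reported at n = 100 per material and at the calculated n if larger, using the pilot's residual variances from the baseline-adjusted model and the correlations among the four comparisons, at zero true difference and at a small prespecified range of differences in both directions. This figure excludes the 6-hour persistence criterion and the superiority comparison with a negative control.

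The cost is a few words, one short calculation from data the pilot already collects, and possibly a less favourable stated figure. No extra pilot subjects are needed.

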9.7.1 Statistical Methods

The Minitab® Version 18 statistical computer package will be used for all statistical calculations.

Non-Inferiority Analysis

An analysis of the data will be performed to determine the non-inferiority of the two test products to the Positive Control. Separate analyses will be performed for data sets for both the abdomen and the inguinal test sites and for the 30-seconds and 10-minutes post-application sample time. Only those data from sites meeting the baseline criteria (3.0 - 5.5 \log_{10} CFU/cm² from the skin of the abdomen and 5.0 - 7.5 \log_{10} CFU/cm² from the skin of the inguen) will be used in the analysis.

The statistic to be used is a multiple linear regression with one quantitative and one qualitative predictor. It has the form:

$$\hat{y} = B_0 + B_1 x_1 + B_2 x_2 + e$$

where:

\hat{y} = \log_{10} Recoveries

B_0 = y intercept

B_1 = Regression slope

B_2 = Difference between the two products

x_1 = \log_{10} Baseline

x_2 = Products

1, if Test Product

2, if Positive Control

e = Error term

The average treatment effect (ATE) is the mean of the 95% confidence interval. For the non-inferiority test, the upper bound of the 95% confidence interval must be equal to or less than 0.5 \log_{10} .

For the non-inferiority test:

$$\bar{x}_C - \bar{x}_T \leq 0.5$$

where:

\bar{x}_T = mean of the test product

\bar{x}_C = mean of the positive control product

0.5 = non-inferiority margin

Descriptive statistics will be generated, including sample sizes, means, standard deviations, and ranges of the recovery data.

Sample Size Determination Analysis

When the study is complete, the PASS 16 statistical package will determine the number of subjects used in a pivotal study for the abdominal and inguinal regions.

The formula that will be used is:

$$n \geq \frac{2 s^2 (z_{\alpha/2} + z_{\beta})^2}{0.5^2}$$

where:

n = minimum number of subjects employed in the study

2 = number of products tested; 3 test materials (Test Product #1, Test Product #2 and Positive Control)

s^2 = the largest variance of the two products tested at the abdominal or inguinal sites

$z_{\alpha/2} = 1.96$ (z-scale) for $1 - 0.05 = 95\%$ confidence of Type I error

$z_{\beta} = 0.842$ (z-scale) for $1 - 0.20 = 0.80\%$ confidence of Type II error

0.5 = Detection level requirement

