2.0 PROTOCOL SYNOPSIS

Name of Sponsor: Professional Disposables International, Inc. (PDI)	Protocol Number 1810480-103.01
Name and Concentration of Test Product Active Ingredients: 26 mL Chlorhexidine Gluconate 3.15% (w/v) and Isopropyl Alcohol 70% (v/v) solution 5.1 mL Chlorhexidine Gluconate 3.15% (w/v) and Isopropyl Alcohol 70% (v/v) solution	
Title of Study:	Pilot Evaluation of Two Test Materials with a Positive Control When Used as a Patient Preoperative Skin Preparation
Principal Investigator:	[name]
Sub-Investigators:	[name], CCRC, [name], CCRP, [name], [name]
Study Center:	BioScience Laboratories, Inc.
Publications (References)	ASTM Standard Test Method E1173-15, Evaluation of Preoperative, Precatheterization, or Preinjection Skin Preparations ASTM E1054-08(2013), Standard Test Methods for Evaluation of Inactivators of Antimicrobial Agents . 2017 FDA, 21 CFR Part 310, Safety and Effectiveness of Health Care Antiseptics; Topical Antimicrobial Drug Products for Over-the-Counter Human Use , Final Rule. (FR82: No. 243, December 20, 2017. pp 60474 to 60503)
Study Duration:	A pre-test period of 14 days and a test period of 1 day.
Objectives:	The purpose of this pilot study is to evaluate the antimicrobial efficacy of two test products containing a chlorhexidine gluconate and isopropyl alcohol solution (26 mL and 5.1 mL), when used as a patient preoperative skin preparation compared to a positive control (Prevantics® Maxi Swabstick 5.1 mL). The evaluation will determine the correct application procedures and the sample size to be used for the pivotal study. The \log_{10} recoveries of the normal flora will be used to determine the antimicrobial effectiveness of the two test materials using a multiple linear regression model, consistent with the requirements of the 2017 FDA 21 CFR

Name of Sponsor: Professional Disposables International, Inc. (PDI)	Protocol Number 1810480-103.01
Name and Concentration of Test Product Active Ingredients: 26 mL Chlorhexidine Gluconate 3.15% (w/v) and Isopropyl Alcohol 70% (v/v) solution 5.1 mL Chlorhexidine Gluconate 3.15% (w/v) and Isopropyl Alcohol 70% (v/v) solution	
	Part 310, Safety and Effectiveness of Health Care Antiseptics; Topical Antimicrobial Drug Products for Over-the-Counter Human Use , Final Rule (December 20, 2017); the difference between the two regression lines is the Average Treatment Effect (ATE).

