
Statistical Methods:
	
A statistical analysis of the data will be performed to determine the non-inferiority of the two test products to the Positive Control. Separate analyses will be performed for data sets for the abdomen and the inguinal test sites and for the 30-seconds and 10-minutes post-application sample times. The statistic to be used is a multiple linear regression with one quantitative and one qualitative variable. The average treatment effect (ATE) is the mean difference of the two products with the 95% confidence intervals in place that will determine if the test products will pass the non-inferiority evaluation. To pass, the upper bounds of the 95% confidence interval must be equal to or less than $0.5 \log_{10}$. The number of subjects necessary to pass this requirement will be determined.
 
Descriptive statistics will be generated, including sample sizes, means, standard deviations, and ranges.

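### The 6-hour effect is a primary variable, but it is evaluated only by a within-product count against baseline; no estimate against the Positive Control is planned at 6 hours

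*Combined protocol and SAP*

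**What the plan says.** The synopsis objective is to evaluate the two test products "when used as a patient preoperative skin preparation compared to a positive control". Section 9.4.3 describes the allocation: "The three test materials will be assigned randomly to the test sites per a computer-generated randomization schedule", with two of the three materials on each subject, one per side. Sampling locations for 30 seconds, 10 minutes and 6 hours are also randomised. Control sites are thus sampled at 6 hours on the same schedule as test sites.

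Section 9.5.3 lists as primary the immediate effects at 30 seconds and 10 minutes "and persistent antimicrobial effects at 6-hours post-application". For the two immediate times the criterion is non-inferiority to the Positive Control with a 0.5 log10 margin. For 6 hours it is that "the 6-hours post-treatment measurement should be lower than or equal to the baseline measurement for 100 percent of the subjects". The synopsis and Sections 9.1 and 9.5.2 repeat this split. Section 7.0 attributes the 100% requirement to the cited 2017 rule, worded there as strictly less than baseline.

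Section 9.7.1 confines the regression on baseline and product to the two immediate times: "Separate analyses will be performed for data sets for both the abdomen and the inguinal test sites and for the 30-seconds and 10-minutes" after application. The synopsis likewise plans it "for the 30-seconds and 10-minutes post-application sample times". Section 9.7.1 contains no 6-hour analysis. It does plan sample sizes, means, standard deviations and ranges of the recovery data, without listing time points.

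**The concern.** A count of sites at or below their own baseline looks at one material at a time. The control result does not enter a test product's verdict, so the count cannot separate a product that holds its effect as well as the control from one that loses it faster. For this one primary variable the plan makes no use of the randomised comparison that its objective calls for.

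At stake is what the pilot can tell its readers. A test product could lie above the control at 6 hours by more than the 0.5 log10 used at the immediate times, meet the persistence rule, and go forward to the pivotal study with no adjusted estimate of the shortfall and no confidence interval. The data that would show it are already being collected.

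**Working it through.** **Plan's own figure.** 75 subjects × 2 sides ÷ 3 materials = 50 sites per material in each region, as the synopsis states.

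**Inputs from the documents.** n = 50 per material and region; margin 0.5 log10; two-sided 95% CI; eligible baselines 3.0–5.5 (abdomen) and 5.0–7.5 (inguen) log10 CFU/cm².

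**Inputs not in the documents.** The 6-hour mean reduction and the SD are not given. Everything below rests on assumed values.

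**Check 1, normal approximation.** With mean 6-hour reduction m and SD of change s, the chance that all 50 sites in a region are at or below baseline is Φ(m/s)^50. For a test product 1.0 log10 worse than control:

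| Control m | Test m | s | Φ(m/s) | Φ(m/s)^50 |
|---|---|---|---|---|
| 3.0 | 2.0 | 0.6 | 0.99957 | 0.979 |
| 3.5 | 2.5 | 0.8 | 0.99911 | 0.957 |
| 4.0 | 3.0 | 1.0 | 0.99865 | 0.935 |

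The rule is not always lenient. A test-product reduction of 2.0 gives 0.732 at s = 0.8, 0.316 at s = 1.0 and 0.086 at s = 1.2.

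**Check 2, simulation** (4000 runs per setting, 50 test and 50 control sites, treated as independent). Baseline is normal with SD 0.6, truncated to the eligible range, with mean 6.0 (inguen) or 4.0 (abdomen). 6-hour recovery = mean − control reduction + deficit + 0.4 × (baseline − mean) + N(0, SD), floored at 0. Share of runs in which a product 1.0 log10 worse than control meets the 100% rule:

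| Region | Control reduction | SD 0.8 | SD 1.0 |
|---|---|---|---|
| Inguen | 3.0 | 63% | 28% |
| Inguen | 3.5 | 93% | 68% |
| Inguen | 4.0 | 99% | 91% |
| Abdomen | 3.0 | 63% | 26% |
| Abdomen | 2.0 | almost never | almost never |

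In the inguinal 3.5 setting, the share falls to 29% at SD 1.25. A product 0.5 log10 worse passes there in 99% (SD 0.8) or 91% (SD 1.0).

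**Both regions.** Section 9.5.3 requires both. Taking inguen 3.5 with abdomen 3.0 and assuming independence: 0.93 × 0.63 ≈ 0.59 at SD 0.8, and 0.68 × 0.26 ≈ 0.18 at SD 1.0.

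**Check 3, what a between-product estimate would show.** Let d be test minus control. The probability that the upper 95% limit is at most 0.5 is Φ((0.5 − d)/(SD × √(2/50)) − 1.96). At d = 1.0 it is below 0.0001 for every SD from 0.6 to 1.2. The CI half-width is 1.96 × SD × √(2/50) = 1.96 × 0.6 × 0.2 = 0.24 at SD 0.6 and 1.96 × 1.2 × 0.2 = 0.47 at SD 1.2. In the simulated inguinal 3.5 setting, the baseline-adjusted regression read as test minus control shows the 1.0-worse product to be worse than control in over 99% of runs. These figures ignore the pairing of two materials within a subject.

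**Check 4, direction.** Section 9.7.1 models log10 recoveries, where higher is worse. It codes the test product 1 and the control 2, and prints control mean minus test mean ≤ 0.5. For a product 1.0 log10 worse, control minus test is −1.0. Even with a half-width of 0.47 the expected upper limit is −1.0 + 0.47 = −0.53, so the worse product passes. Check 3 therefore holds only for test minus control, not for the rule as printed.

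**The case against.** The strongest reply is that persistence is an absolute criterion by design. The efficacy sections state non-inferiority for the two immediate times and then, separately, persistence against baseline, and Section 7.0 attributes both to the cited rule. A product that meets the rule is persistent as the plan defines it, and nowhere does the plan claim persistence relative to the control. This stands: a reader might infer that the plan departs from its own criterion or that the 100% rule is wrong, and the documents support neither.

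A reader might also infer that nothing about the control will be known at 6 hours. That goes too far. Section 4.0 counts the Positive Control as a test material, so it faces the same 100% rule, and the planned descriptive statistics may cover 6 hours. If they do, an unadjusted difference and interval could be worked out by hand. But the time points are not listed, and no adjusted contrast or interval is planned.

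It can be said too that the pilot serves to settle application procedures and pivotal sample size, and that a supporting estimate changes no pass/fail decision. That is true, and it limits the weight of the point. A pilot that informs a pivotal study is nevertheless the place to see a 6-hour shortfall.

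Finally, the 0.80 power in Section 9.7 should not be set against this pilot's precision at 6 hours. It sizes the pivotal study.

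**Conclusion.** The point holds as a gap in what the plan can conclude. A primary variable in a randomised, controlled study is evaluated by a pass/fail count within each product, with no hypothesis test or interval, and no between-product estimate is planned for it. The count can be met by a product well behind the control: about 93% to 68% of runs for a 1.0 log10 deficit in the inguen, assuming a control reduction of 3.5 and residual SD 0.8 to 1.0.

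The size is uncertain. Across the assumed reductions and SDs the figure runs from about 99% to almost never per region, and it is lower when both regions must pass. A reader might infer that an inferior product would usually be passed as persistent. The documents do not support that, because they give neither the reduction nor the SD. What holds whatever those values are is that the verdict does not depend on performance relative to the control. The addition is cheap and worth making.

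**What to change.** 1. **Reconcile the direction in Section 9.7.1 first.** The printed inequality and the product coding must agree with higher recoveries being worse. The regression should not be carried to a third time point as printed.
2. **Add a supporting 6-hour analysis to Section 9.7.1 and the synopsis.** Use the same baseline-adjusted model and report each test product minus Positive Control in log10 recovery, with a 95% CI, separately for abdomen and inguen. State the direction explicitly. Show 0.5 log10 as a reference only.
3. **Keep the 100% rule as the pass/fail criterion**, and say in Section 9.5.3 that it supports a statement about 6-hour counts against baseline. Any statement about persistence relative to the control should rest on the new estimate.
4. **List the time points** covered by the descriptive statistics, including 6 hours.

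The cost is wording in three places and four more model runs (2 products × 2 regions), with no extra subjects, samples or visits. The downside is precision: at 50 sites per material the half-width is about 0.24 to 0.47 log10 for SD 0.6 to 1.2, so the result should be labelled an estimate and not a further hurdle.
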